Eligible VAMC patients will be randomized into one of two treatment conditions: transdiagnostic CBT or an existing evidence-based version of CBT (BAT). Both treatment conditions will include 12-16 weekly 45-60-minute individual psychotherapy sessions. The total number of sessions will vary slightly depending on participant needs and progress during therapy, as is common in most CBT approaches to psychotherapy (and will serve as a covariate in the outcome analyses). The general format of sessions will involve: 1) brief check-in; 2) review of materials from previous sessions; 3) review of homework assignments; 4) overview of new materials and insession exercises; and 5) assignment of homework for next session. Attendance and homework completion will be recorded. A full battery of self-report questionnaires and a diagnostic interview will be completed pretreatment, post-treatment, and at the 6-month follow-up to track participants' progression through treatment and maintenance. Post-treatment participant interviews will be completed at immediate post-treatment and 6-month follow-up to collect feedback on participants' perspectives on the treatments.

Table of Procedures for Each Visit – Summarized Across Treatment Conditions

Week	Content	Assessment Summary
1	Pre-Treatment Assessment	Clinical interview & self-report battery (7 measures)
2	Session 1: Psychoeducation	Brief self-report battery (3 measures)
3 4 5	Session 2: Treatment planning Session 3: Introduction to behavior therapy Session 4: Behavior therapy	Brief self-report battery (3 measures)
6	Session 5: Behavior therapy	Brief self-report battery (3 measures)
7 8	Session 6: Behavior therapy Session 7: Behavior therapy	Brief self-report battery (3 measures)
9 10 11	Session 8: Behavior therapy Session 9: Behavior therapy Session 10: Behavior therapy	Brief self-report battery (3 measures)
12 13	Session 11: Behavior therapy Session 12: Behavior therapy	Brief self-report battery (3 measures)
14	Session 13: Behavior therapy (as needed)	Brief self-report battery (3 measures)
15 16 17	Session 14: Behavior therapy (as needed) Session 15: Behavior therapy (as needed) Session 16: Relapse prevention (as needed)	Brief self-report battery (3 measures)
~18	Post-Treatment Assessment	Clinical interview, immediate treatment interview, & self-report battery (7 measures), treatment satisfaction

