In preliminary hypothesis testing, efficacy outcome variables will be compared using the generalized linear mixed models (GLMM) approach. This approach provides a general framework that accommodates a wide range of data types (continuous, ordinal, dichotomous, categorical, count) and distributional assumptions (e.g. Gaussian, Binomial, Poisson) and accommodates repeated measures, covariate structure among repeated observations, and missing data. In the first set of primary hypothesis testing analyses, immediate post-treatment scores for each outcome of interest will be used (separately) as the dependent variable in the model, intervention (transdiagnostic CBT versus BAT control) will be included as the primary independent variable, and pre-treatment scores for the outcome of interest will be added as covariates. When approximate normality is assumed, GLMM reduces to a general linear models (GLM) approach which, in the simplest case (intervention as the primary independent variable with baseline level of outcome variable as covariate), is equivalent to a comparison of change from baseline scores for transdiagnostic CBT versus BAT control using an independent sample t-test. Additional covariates (e.g. age, number of psychiatric comorbidities, race, sex, combat theatre, and number of treatment sessions) will be added to the model to adjust for putative confounding variables. If intervention differences in other baseline variables are found in initial descriptive analyses, these variables will be also be added to the multivariable model. In secondary analyses, the modeling procedure will be repeated for the period between immediate post-treatment and 6-month follow-up. Given that we are seeking preliminary evidence of treatment

efficacy (to justify the next step in this line of research), there will be no adjustment for multiple outcomes or time points to avoid an overly conservative approach at this preliminary stage.

Feasibility and Acceptability Analyses (Primary Aim 2)

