Measures of feasibility and acceptability are dropout proportions (dropout y/n), proportion of sessions attended, proportion of homework assignments completed, and patient satisfaction scores on the STTS-R. 95% CI for proportions will be used to estimate the proportion of participants who exit the study prematurely (drop out) within each intervention group and the difference in dropout proportions between the intervention groups. For the treatment satisfaction and adherence outcomes (STTS-R, proportion of missed sessions or homework assignments), the median and mean responses will be obtained within and between each intervention group. 95% CI for difference in means will be used to estimate the between intervention differences in treatment satisfaction (mean STTS-R) and adherence (e.g. average proportion of missed sessions or homework assignments) for the transdiagnostic CBT versus BAT control conditions. Frequency distributions describing the participants' reasons for noncompliance and discontinuation of participation will be developed.

The GLMM modeling framework described for Primary Aim 1 will be used to compare the effect of transdiagnostic CBT versus BAT control on treatment satisfaction, retention (dropout), and treatment adherence (% missed sessions, % homework completion). Dropout proportions (dichotomous outcome) and % of missed visits and % homework completion will be compared between the intervention groups using GLMM, with logistic/binomial regression analyses as special cases for dichotomous and percentage outcomes; STTS-R will be modeled as a continuous outcome using an appropriate link function. We also will model the longitudinal profile of adherence as a dichotomous outcome at each visit (e.g. attended/did not attend a given session). This will allow us to evaluate the trends in session attendance and to determine if the trends differ by intervention (e.g. whether the probability of missing visits is less/greater at earlier or later time points).

Exploratory Analyses - Diagnostic Groups

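### The model-based test of percentage missed sessions and percentage homework states no allowance for within-person correlation; fitted as plain binomial regression it would be anti-conservative

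*Combined protocol and SAP*

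**What the plan says.** All the analysis text on this point is in section D, Feasibility and Acceptability Analyses (Primary Aim 2).

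- **Estimation.** For adherence, "95% CI for difference in means will be used to estimate the between intervention differences", and the quantity is the "average proportion of missed sessions or homework assignments". Here each participant contributes one proportion.
- **Testing.** "The GLMM modeling framework described for Primary Aim 1 will be used to compare the effect of transdiagnostic CBT versus BAT control" on satisfaction, retention and adherence. For the dichotomous and percentage outcomes the sentence continues "with logistic/binomial regression analyses as special cases for dichotomous and percentage outcomes". The Primary Aim 1 section describes the framework as one that "accommodates repeated measures, covariate structure among repeated observations, and missing data".
- **Per-visit model.** "We also will model the longitudinal profile of adherence as a dichotomous outcome at each visit", illustrated as "attended/did not attend a given session". No correlation structure is given.

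The Procedures section allows 12 to 16 sessions. In the Table of Procedures for Each Visit, sessions 13 to 16 are conditional, for example "Session 13: Behavior therapy (as needed)". No section gives the denominator for the percentage of missed sessions or says how sessions after dropout are scored. The Missing Data section plans multiple imputation but does not say whether attendance after dropout is a missing value or a missed session.

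**The concern.** A participant's sessions are not independent trials. Some people attend reliably and some do not, and anyone who leaves early attends none of the later sessions. A binomial likelihood with only an intervention term sets the variance of each person's count from the mean alone. When people differ, the real variance is larger, so the standard error is too small and the p-value too low.

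Missed sessions and homework are two of the four feasibility measures listed for Primary Aim 2, and Hypothesis 2 names better attendance among its evidence. A plain binomial p-value could therefore declare an attendance advantage while the planned interval for the same contrast, built on participant means, includes zero. The plan does not say which of the two would govern.

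**Working it through.** The plan states no standard error, intraclass correlation (ICC) or adherence rate for these outcomes, so there is no figure of its own to reproduce.

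**Inputs from the documents**
- Sessions per person, m: 12 to 16 (Procedures).
- 48 per arm (Randomization Procedures).
- Non-completion: 3/15 = 20% and 8/31 = 25.8% in the two demonstrations (Preliminary Studies); up to 24/96 = 25% by the completer target (Recruitment Strategy).

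**Assumed:** the ICC, a 10% chance of missing a session while in treatment, and exit at a uniformly random session.

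**1. Design effect, m sessions counted for everyone.** Naive SE / correct SE = 1/√(1 + (m − 1) × ICC). The actual two-sided error of a nominal 5% test is about 2 × (1 − Φ(1.96 × ratio)).

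| ICC | ratio, m = 12 | ratio, m = 16 | error, m = 12 |
|---|---|---|---|
| 0 | 1.00 | 1.00 | 5% |
| 0.05 | 1/√1.55 = 0.80 | 1/√1.75 = 0.76 | 12% |
| 0.10 | 1/√2.10 = 0.69 | 1/√2.50 = 0.63 | 18% |
| 0.20 | 1/√3.20 = 0.56 | 1/√4.00 = 0.50 | 27% |

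A ratio of exactly one half needs 1 + (m − 1) × ICC = 4, so ICC = 3/11 = 0.27 at m = 12 or 3/15 = 0.20 at m = 16.

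**2. Sessions after dropout counted as missed (m = 12, no other correlation).** Let a dropout be due K sessions before exit, K uniform on 1 to 11, with mean 6 and variance (121 − 1)/12 = 10.
- Dropout: mean missed = 12 − 0.9 × 6 = 6.6; variance = 0.81 × 10 + 0.09 × 6 = 8.64.
- Completer: mean missed = 1.2; variance = 12 × 0.09 = 1.08.
- At 20% dropout: mean = 0.2 × 6.6 + 0.8 × 1.2 = 2.28, so the missed rate is 2.28/12 = 0.19. Variance = 0.2 × 8.64 + 0.8 × 1.08 + 0.2 × 0.8 × 5.4² = 7.26. The binomial variance is 12 × 0.19 × 0.81 = 1.85. Dispersion = 7.26/1.85 = 3.9; SE ratio = 1/√3.9 = 0.50.
- At 25.8% dropout, the same steps give mean 2.59, variance 8.61, binomial variance 2.03, dispersion 4.2 and SE ratio 0.49.

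The error formula in step 1 then gives about 32-34%.

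**3. Simulation with no true difference, 48 per arm, m = 12.**
- Denominator stops at exit, no person-level correlation: dispersion 1.0; rejection about 5%.
- Denominator stops at exit, ICC 0.05 / 0.10 / 0.20: rejection 9-12% / 15-18% / about 26%.
- Sessions after dropout counted as missed, 20-26% dropout: rejection 32-40%; dispersion 3.9-5.3. With m = 16 the SE ratio falls to 0.40-0.44 and rejection rises to 39-44%.
- A quasi-binomial test, or a comparison of participant proportions, stayed at roughly 4-6% throughout.

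Homework was not calculated separately, because the documents give no count of assignments. The direction is the same; the size is not established.

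**The case against.** The strongest answer is that the plan does not choose independence. It names GLMM first and carries over a framework said to handle repeated measures; binomial regression may identify only the distribution and link, leaving room for a participant random effect. That reading is permissible, so a reader who infers that the plan commits itself to treating sessions as independent goes further than the text. It does not remove the gap. A percentage is one record per person, so extra-binomial variation has to be added deliberately, and the plan names nothing that adds it.

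Three other objections have force.

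- **The planned intervals are sound.** They compare means of participant proportions, so within-person dependence is already absorbed. Dropout is one yes/no per person and the STTS-R is a score per person. A claim that the error bars for Primary Aim 2 as a whole are about half the right width is not supported.
- **The size depends on the denominator.** If sessions are counted only to exit and people do not otherwise differ, the inflation vanishes. Counting later sessions as missed creates most of the overdispersion and partly repeats the separate dropout outcome. It would also score as missed the sessions that follow an exit decided by a clinician, which the Potential Risks section allows for.
- **The as-needed sessions.** A reader might infer that someone who finishes at session 12 is coded a non-attender at sessions 13 to 16. Nothing says so; the note to the procedures table sets the final session by joint decision, so such a person has no session 13 to miss. What stands is that the coding is not defined and that any trend over the last sessions rests on those who continued.

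**Conclusion.** The concern holds for the model-based comparison of percentage missed sessions and percentage homework, and for any interval taken from that model. Fitted as plain binomial regression, it is anti-conservative for every positive within-person correlation; that direction needs no assumed figure. For missed sessions, the size is about 10-26% false positives at an assumed ICC of 0.05-0.20 with sessions counted to exit. It is about 30-40%, with standard errors about half the right size, only if sessions after dropout count as missed. Half width is thus one point in a range set by an ICC and a denominator that the documents do not give. This is an underspecified test with a known bad default. It should be settled before the adherence data are analysed.

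**What to change.** - Test the two percentage outcomes with a quasi-binomial or beta-binomial model, or with the participant-level comparison of means that matches the planned interval. State which result governs.
- Put a participant random intercept in the per-visit attendance model.
- Fix the session denominator in advance: whether sessions after dropout are missed, excluded or imputed; how exits not initiated by the participant are scored; and whether as-needed sessions 13 to 16 that were never scheduled are left out. Sessions 1 to 12, which are scheduled in both arms without the as-needed label, would give a common base.

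The cost is a few sentences in the analysis plan and no new data. The downside is wider model-based intervals and larger p-values for these two outcomes.

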1. RISKS TO THE SUBJECTS

a. Risks to the Subjects

Participants will include 96 VAMC patients in the mental health service. The inclusion criteria are that participants must: 1) be an adult (18 – 80 years old), 2) be competent to provide informed consent for research participation, 3) be diagnosed with an depressive/anxiety disorder as determined by a semi-structured diagnostic assessment (ADIS-5) at pre-treatment assessment, and 4) be able to commute to the RHJ VAMC for weekly appointments, immediate post-treatment assessment, and a follow-up assessment at 6-months post-treatment.

Several exclusion criteria exist for the proposed investigation, including 1) recent history (≤ 2 months) of psychiatric hospitalization or a suicide attempt as documented in their medical record, 2) current diagnosis of substance dependence or abuse on the structured clinical interview, 3) acute, severe illness or medical condition that likely will require hospitalization and/or otherwise interfere with study procedures as documented in their medical record (e.g., active chemotherapy/radiation treatment for cancer, kidney dialysis, oxygen therapy for chronic obstructive pulmonary disease), 4) recent start of new psychiatric medication (≤ 4 weeks), 5) diagnosis of traumatic brain injury in their medical record and/or endorsement of screener questionnaire regarding the symptoms of TBI modified from the Post-Deployment Health Assessment employed by the Department of Defense, or 6) diagnosis of schizophrenia, psychotic symptoms, personality disorder, and/or bipolar disorder.

VAMC patients excluded due to these factors will be reconsidered for participation once the condition related to their exclusion is resolved or stabilized.

Targeted/Planned Enrollment Table

Total Planned Enrollment 96

TARGETED/PLANNED ENROLLMENT: Number of Subjects								
		Sex/Gende	r					
Ethnic Category	Females Males Tota							
Hispanic or Latino	2	6	8					
Not Hispanic or Latino	22	66	88					
Ethnic Category: Total of All Subjects*	24	72	96					
Racial Categories								
American Indian/Alaska Native	0	0	0					
Asian	1	5	6					
Native Hawaiian or Other Pacific Islander	0	0	0					
Black or African American	9	25	34					
White	14	42	56					
Racial Categories: Total of All Subjects*	24	72	96					

b. Sources of Materials

All participants will randomized into either a transdiagnostic CBT psychosocial treatment for the depressive/anxiety disorders or the comparison evidence-based CBT, Behavioral Activation Treatment (BAT), control condition. The transdiagnostic CBT is a variation of pre-existing psychosocial treatments that are regularly administered at the VAMC and will involved 12-16 weekly 45-60-minute individual therapy appointments. The protocol for the BAT condition will be consistent with approaches that have been shown to be effective in the past literature. Throughout the course of treatment, a multi-method assessment of psychosocial factors and quality of life will be completed for all participants, involving 1) treatment credibility and satisfaction, 2) treatment retention and adherence, 3) clinical symptomatology including anxiety, depression, and impairment, and 4) general feedback on treatment process. Participants will be paid \$10 for completing the self-report questionnaires and an additional \$10 for the completion of the ADIS-5 for a possible combined total of \$60. In addition to the pre-treatment, immediate post-treatment, and 6-month follow-up assessments with the full battery, a brief assessment involving a few self-report measures (e.g., DASS, IIRS, & STICSA) will be completed biweekly to monitor symptoms during the course of treatment.

- 1. *Demographic Information*: Age, race, sex, education, employment, and combat experience will be collected via a study specific demographic form.
- Albany Panic and Phobia Questionnaire. The APPQ is a 27-item self-report measure that assesses agoraphobia, social anxiety, and interoceptive avoidance. Each subscale has been shown to have good internal consistency (*α*s > .85) and temporal stability (*r*s > .87).
- 3. Anxiety Disorder Interview Schedule-5. The ADIS-5 is a well-established, semi-structured interview designed to assess a wide range of Axis I disorders. The ADIS-5 assesses current and past diagnoses with DSM diagnostic criteria, severity scores, and lists of feared and avoided situations for the anxiety disorders. The ADIS has demonstrated excellent inter-rater reliability and validity of depressive/anxiety disorder diagnoses. The ADIS-5 is currently in press and so an editor's copy provided in the appendix (with editor's comments). The PHI (e.g., name, address, contact information, DOB) on the demographics cover page (page 1) will be removed in the study copy.
- 4. Depression Anxiety Stress Scales 21-Item Version. The DASS is a 21-item measure with three subscales designed to assess dysphoric mood, fear and autonomic arousal, and tension and agitation. The factor structure, reliability, and validity of the subscales have been supported in the literature. The DASS scales also

have demonstrated excellent convergence with similar measures of depression and anxiety and high internal consistency ($\alpha > .85$).

- 5. *Illness Intrusiveness Ratings Scale.* The IIRS is a 13-item questionnaire that assesses the extent to which a disease interferes with important domains of life, including health, diet, work, and several others. Each item is rated on a 7-point Likert scale, ranging from 1 to 7, and summed to compute the scale score. The IIRS has been shown to have high internal consistency in the previous literature and present study (α = .88).
- 6. Multidimensional Assessment of Social Anxiety. The MASA is a 38-item self-report measure that was designed to assess trait symptom dimensions consistent with the hybrid model of social anxiety. The psychometric properties of the MASA are supported in the literature, including its factor structure, convergent and discriminant validity, test-retest reliability, and internal consistency. The internal consistency was found to be acceptable for each of the scales in the present study (*α*s > .71).
- 7. *Mini International Neuropsychiatric Interview*. The MINI is a structured diagnostic interview designed to provide a brief, but accurate, assessment of a wide range of Diagnostic and Statistical Manual (DSM-IV) psychiatric disorders, including the mood disorders, anxiety disorders, and substance use disorders. The MINI has demonstrated adequate inter-rater and test-retest reliability across most disorders, and specifically has shown good inter-rater reliability with a GAD SCID diagnosis ($\kappa = 0.7$). DSM-IV diagnostic criteria, including hierarchy rules, were used to establish diagnoses. The PHI (e.g., name and DOB) in the header will be removed in the study copy.
- 8. *PTSD Checklist*. The PCL is a 17-item measure designed to assess PTSD symptom severity related to military/combat-related trauma. Respondents are presented with 17 specific symptoms of PTSD and asked to rate "how much you have been bothered by that problem in the last month" on a 5-point Likert scale, ranging from 1 (not at all) to 5 (extremely). The PCL has been shown to have excellent internal consistency in veterans, victims of motor vehicle accidents, and sexual assault survivors (α s > .94) and excellent test-retest reliability in veterans (*r* = .96). In addition, the PCL has demonstrated excellent convergent validity with alternative measures of PTSD (rs range from .77 to .93). Due to the PCL's focus on DSM-IV diagnostic criteria, a revised PCL for DSM-5 criteria will be included when made available by the authors.
- Satisfaction with Therapy and Therapist Scale Revised. The STTS-R assesses patients' level of satisfaction with their therapeutic experiences. The STTS-R contains 12 items that represent two subscales: satisfaction with therapy and satisfaction with therapist. The measure has been investigated in a large sample of patients receiving group CBT for depressive/anxiety disorders. The two subscales have demonstrated excellent internal consistency (αs > .88) and high positive correlations with indicators of successful treatment outcome.
- 10. State-Trait Inventory for Cognitive and Somatic Anxiety Trait Version. The STICSA-Trait is a 21-item measure that assesses trait cognitive and somatic anxiety. The cognitive and somatic subscales have been supported in the literature and both subscales have high internal consistency (αs > .87). In addition, the STICSA-Trait scale was found to remain stable over repeated administrations during several stress manipulations (*r*s > .65).
- 11. Veterans Short-Form Health Survey. The V/SF-36 is a 36-item measure designed to assess functional health, well being, and quality of life in Veterans, and can be scored to produce two primary subscales for physical health and mental health. The V/SF-36 was adapted from the original SF-36, which has received extensive support in the literature.

Participants will be asked to complete the assessment materials three times throughout the duration of treatment: pre-treatment, post-treatment and six-month follow-up.

c. Potential Risks

There is a potential psychological risk of emotional discomfort during the assessment and treatment procedures. Although this reaction is not uncommon in exposure-based treatments of anxiety and depression and typically is brief in its duration, there are several provisions to reduce and/or avoid it in the proposed study. First, the proposed treatment will be designed specifically to target the reduction of emotional distress, anxiety, and avoidance. Second, if a participant expresses a desire to discontinue treatment due to distress and/or a study clinician determines that participation is counter-indicated, all research and treatment procedures will be terminated.

